APPENDIX 4. BLOOD VOLUMES TO BE DRAWN

Total Volume of Blood to be Drawn from Each Subject in Part A				
Assessment		Sample Volume (mL)	Number of Samples	Total Volume (mL)
Viral screen (HIV, HBV, HCV)		8.5	1	8.5
Safety	Serum chemistry, CRP, β -hCG ^a	8.5	9	76.5
	Hematology	4.0	9	36.0
	Coagulation	4.5	9	40.5
██████████	mRNA assay	5.0	6	30.0
██████	assay	2.5	6	15.0
CFTR and PEG antibody assay		4.0	6 ^b	24.0
CFTR T cell assay		20.0	6 ^b	120.0
Total Volume for Study (mL)		-	-	350.5

β -hCG=beta-human chorionic gonadotropin; CRP=C-reactive protein; HIV=human immunodeficiency virus; HBV=hepatitis B virus; HCV=hepatitis C virus.

^a Female subjects only.

^b Includes the optional blood sample to be collected on the final study day (Day 337 in Part A), if needed for assessment of immune responses to CFTR protein (Section 7.5.2.15).

Total Volume of Blood to be Drawn from Each Subject in Part B				
Assessment		Sample Volume (mL)	Number of Samples	Total Volume (mL)
Viral screen (HIV, HBV, HCV)		8.5	1	8.5
Safety	Serum chemistry, CRP, β -hCG ^a	8.5	11	93.5
	Hematology	4.0	11	44.0
	Coagulation	4.5	11	49.5
Inflammatory markers ^c		1.0	6	6.0
██████████	mRNA assay	5.0	8	40.0
██████	assay	2.5	8	20.0
CFTR and PEG antibody assay		4.0	6 ^b	24.0
CFTR T cell assay		20.0	6 ^b	120.0
Total Volume for Study (mL)		-	-	405.5

β -hCG=beta-human chorionic gonadotropin; CRP=C-reactive protein; HIV=human immunodeficiency virus; HBV=hepatitis B virus; HCV=hepatitis C virus.

^a Female subjects only.

^b Includes the optional blood sample to be collected on the final study day (Day 365 in Part B), if needed for assessment of immune responses to CFTR protein (Section 7.5.2.15).

^c Inflammatory markers to be collected in the 20 mg dose group only.

Total Volume of Blood to be Drawn from Each Subject in Part D				
Assessment		Sample Volume (mL)	Number of Samples	Total Volume (mL)
Viral screen (HIV, HBV, HCV)		8.5	1	8.5
Safety	Serum chemistry, CRP, β -hCG ^a	8.5	11	93.5
	Hematology	4.0	11	44.0
	Coagulation	4.5	11	49.5
Inflammatory markers		1.0	8	8.0
[REDACTED] mRNA assay		5.0	13	65.0
[REDACTED] assay		2.5	13	32.5
CFTR and PEG antibody assay		4.0	7 ^b	28.0
CFTR T cell assay		20.0	7 ^b	140.0
Total Volume for Study (mL)		-	-	469.0

β -hCG=beta-human chorionic gonadotropin; CRP=C-reactive protein; HIV=human immunodeficiency virus; HBV=hepatitis B virus; HCV=hepatitis C virus.

^a Female subjects only.

^b Includes the optional blood sample to be collected on the final study day (Day 341 in Part D), if needed for assessment of immune responses to CFTR protein (Section [7.5.2.15](#)).

**DOCUMENT VERSION CONTROL**

Version Number	Date	Comments/Changes
1.0	26 October 2021	Initial Version

[figure not shown]

## **LIST OF ABBREVIATIONS**

AE	adverse event
BMI	body mass index
CF	cystic fibrosis
CFQ-R	cystic fibrosis questionnaire-revised
CFTR	cystic fibrosis transmembrane conductance regulator
CSR	clinical study report
ECG	electrocardiogram
FEF	forced expiratory flow
FEV 1	forced expiratory volume in 1 second
hCFTR	human cystic fibrosis transmembrane conductance regulator
ICH	International Council for Harmonisation
MAD	multiple ascending dose
MedDRA	Medical Dictionary for Regulatory Activities
PEF	peak expiratory flow
PSRC	Protocol Safety Review Committee
qPCR	quantitative polymerase chain reaction
SAD	single ascending dose
SAE	serious adverse event
SAP	statistical analysis plan
SD	standard deviation
SUSAR	suspected unexpected serious adverse reaction
TEAE	treatment-emergent adverse event
ULN	upper limit of normal

## **1. PURPOSE OF THE ANALYSES**

The statistical analysis plan (SAP) is being developed after review of the Translate Bio, Inc., protocol number MRT5005-101, but before the final analyses of the data. The SAP contains detailed information to aid in the implementation of the statistical analyses and reporting of the study data for use in the clinical study report (CSR).

This SAP is being written with due consideration of the recommendations outlined in the most recent International Council for Harmonisation (ICH) E9 Guideline entitled Guidance for Industry: Statistical Principles for Clinical Trials and the most recent ICH E3 Guideline, entitled Guidance for Industry: Structure and Content of Clinical Study Reports.

This SAP describes the analysis sets that will be analyzed, the subject characteristics parameters, and the safety parameters that will be evaluated. The details of the specific statistical methods that will be used are provided in the SAP. Table, figure, and listing specifications are provided in separate documents.

## **2. PROTOCOL SUMMARY**

### **2.1 Study Objectives**

#### **2.1.1 Primary Objective**

To evaluate the safety and tolerability of single and multiple escalating doses of MRT5005 administered by nebulization to adult subjects with cystic fibrosis (CF).

#### **2.1.2 Secondary Objective**

To evaluate the effect on percent predicted forced expiratory volume in 1 second (ppFEV1) and other spirometry parameters after single and multiple escalating doses of MRT5005 administered by nebulization to adult subjects with CF.

### **2.2 Study Endpoints**

#### **2.2.1 Primary Endpoint**

The safety and tolerability of nebulized MRT5005 will be assessed based on the types, frequency, and severity of treatment-emergent AEs including pulmonary exacerbations; concomitant medication use; and changes from baseline in physical examination, weight, vital signs, oxygen saturation (pulse oximetry), ECG, standard clinical laboratory tests, chest x-ray, and spirometry as a measure of pulmonary function.

#### **2.2.2 Secondary Endpoint**

The biological activity of nebulized MRT5005 will be assessed based on changes from baseline in ppFEV1 and other spirometry parameters.

### **2.3 Overall Study Design and Plan**

This phase 1/2 study is designed as a randomized, double-blind, placebo-controlled, combined single and multiple ascending dose (SAD and MAD) trial, which will be conducted in 3 parts. Subjects will be administered single and multiple escalating doses of MRT5005 in Parts A and B of the study, respectively. In Part D, subjects will be administered 5 consecutive daily doses of 4 mg MRT5005 or placebo. Part C (bronchoscopy groups) was removed from the protocol in the 3rd amendment to the protocol (Version 4.0 dated 29 July 2019).

The study will be conducted at multiple centers in the United States with expertise in treating CF subjects. At least 40 adult male and female subjects with CF, 18 years of age or older, are planned to participate in the study. Subjects who are clinically stable with a forced expiratory volume in 1 second (FEV1)  $\geq 50\%$  and  $\leq 90\%$  predicted, and who meet all inclusion criteria and none of the exclusion criteria, will be eligible for the study. The inclusion and exclusion criteria for the study are enumerated in [Sections 4.1](#) and [4.2](#) of the protocol, respectively. Women of childbearing potential will also be eligible to participate if they are willing and able to comply with contraception requirements.

If subjects do not complete the study or complete certain procedures, additional subjects will be enrolled at the Sponsor's discretion to ensure that at least 16, 16, and 8 evaluable subjects complete Parts A, B, and D of the study, respectively. For Part A, an evaluable subject will be defined as a subject with 1 completed dose and 4 weeks of safety follow-up. For Part B, an evaluable subject will be defined as a subject with 4 completed doses occurring on 4 consecutive weeks with 4 weeks of safety follow-up. For Part D, an evaluable subject will be defined as a subject with 4 completed doses occurring within 5 consecutive days with 4 weeks of safety follow-up. A SAD dose group may be repeated in a new group of subjects in Part A to further assess the safety of the dose level before escalating to the next higher dose level, or before allowing it to proceed from Part A (SAD) to Part B (MAD). It is expected that no more than 1 additional group of 4 subjects will be enrolled into the study in Part A. Therefore, up to a maximum of 44 evaluable subjects may participate in the study.

Each part of the study will consist of a screening period, a treatment period, and a follow-up period. Multiple visits during the screening period, from Day -28 to Day -2 (Parts A and B) or from Day -28 to Day -1 (Part D), may be necessary for the subject to complete all of the required screening procedures and tests. During the treatment period, subjects participating in Part A will be confined to the study center from Day -1 to Day 2 and will receive a single dose of investigational product. This will be followed by a safety follow-up period, which continues up to the final study visit on Day 337. During the safety follow-up, clinic visits for Part A subjects will be performed on an outpatient basis.

No confinement will be required of subjects in Parts B and D of the study; these subjects will perform all clinic visits in the treatment and follow-up periods as outpatients. During the treatment period of Part B (Day -1 to Day 33), subjects will receive 5 doses of investigational product, administered 1 dose per week for 5 weeks. During the treatment period of Part D (Day 1 to Day 5), subjects will receive 5 doses of IP, administered 1 dose per day for 5 days. The safety follow-up period will continue up to the last study visit on Day 365 for Part B and Day 341 for Part D.

In Part A (SAD groups), 4 groups consisting of 4 subjects each will be enrolled sequentially to receive single doses of MRT5005 or placebo (normal saline) administered by nebulization. Three dose levels of MRT5005 were planned to be investigated: 8, 16, and 24 mg of [REDACTED]

[REDACTED] mRNA [REDACTED] mRNA (the active drug substance of MRT5005; nominal doses)]. An additional treatment group (20 mg) was added after blinded safety information from the 24 mg dose group revealed the occurrence of febrile reactions in 3 of 4 subjects. Within each dose group, the enrollment and treatment of the 4 subjects will be staggered by at least 1 week. Subjects will be randomized in a 3:1 ratio to receive a single dose of either MRT5005 or placebo (3 subjects to receive MRT5005 and 1 subject to receive placebo per dose group).

The protocol safety review committee (PSRC) will be responsible for reviewing safety data and, based on this review, making the decision to dose escalate from the 8 mg starting SAD dose level to the 16 mg dose level, and then to the 24 mg maximum dose level. The 20 mg dose level will be evaluated after the 24 mg dose level.

The decision to begin enrollment and treatment of the initial 8 mg multiple-dose group in Part B will also be made by the PSRC, based on a review of at least 28 days of safety follow-up for all subjects who received a single dose of the 8 mg dose level in Part A.

In Part B (MAD groups), 4 groups consisting of 4 subjects each will be enrolled sequentially to receive multiple doses of MRT5005 or placebo administered by nebulization. Three groups will be enrolled sequentially to receive dose levels of MRT5005 investigated as single doses in Part A (8, 16, and 20 mg). An additional dose level that was not investigated in Part A (12 mg) will also be evaluated in Part B. The 12 mg dose group may be enrolled in parallel with the 16 and/or 20 mg dose group. Within each dose group, subjects will be randomized in a 3:1 ratio to receive 5 doses of either MRT5005 or placebo (3 subjects to receive MRT5005 and 1 subject to receive placebo per dose group), administered 1 dose per week for 5 weeks. The enrollment and treatment of the 4 subjects within each dose group will be staggered by at least 2 weeks (the next subject in the dose group will be enrolled and treated only when the previous subject has received their second dose and at least 1 week of safety follow-up), with the exception of the 12 mg dose group in Part B which may not require staggered treatment as outlined in Protocol [Section 3.1](#).

Similar to Part A, the PSRC will be responsible for reviewing safety data and making the decision to dose escalate.

In Part D, 8 subjects will be randomized in a 3:1 ratio to receive 5 doses of either 4 mg MRT5005 or placebo, administered at 1 dose per day for 5 consecutive days.

Because single doses up to 20 mg, as well as 5 weekly doses up to 16 mg have been tolerated in Parts A and B, the enrollment and treatment of the 8 subjects within Part D will not be staggered.

All subjects in the study will be monitored for safety for 12 months after administration of the last dose of investigational product (post-single dose in Part A; post-fifth dose in Parts B and D). The safety and tolerability of nebulized MRT5005 will be assessed based on the types, frequency, and severity of treatment-emergent adverse events (TEAEs) reported including the number of pulmonary exacerbations; concomitant medication use; and changes from baseline in physical examination, weight, vital signs, oxygen saturation (pulse oximetry), electrocardiogram (ECG), standard clinical laboratory tests, chest x-ray, and spirometry as a measure of pulmonary function. As part of the safety evaluation, assays to detect [REDACTED] mRNA and [REDACTED] in the blood post-treatment will be performed along with assays to detect antibody and T cell immune responses to CFTR protein and anti-PEG (polyethylene glycol) antibodies.

This will be conducted as a double-blind study, except for the last part of the 12-month follow-up. All subjects in the study will be followed up for 12 months after their last dose, but the treatment randomization for the 8, 16, and 24 mg single dose groups will be unblinded 1 month after the last dose of the last subject in the 24 mg single dose group in Part A. The blind will be maintained in the 20 mg single dose group in Part A, as well as the 8, 16, and 12 mg multiple dose groups in Part B until the 1-month time point after the last dose (Day 57) of

the last subject dosed in the 12 mg dose group. For the 20 mg multiple dose group in Part B, the blind will be maintained until the last subject in this group has reached the 1-month time point after the last dose day (Day 57). For Part D, the blind will be maintained until the 1-month time point after the last dose (Day 32) of the last subject in Part D.

During the double-blind period, the investigators and all study staff involved in the evaluation of subject eligibility, administration of IP, and assessment of the study outcomes will be blinded to treatment assignment (MRT5005 vs. placebo within each dose group) until planned unblinding. All subjects and their families, as well as sponsor personnel in direct contact with the study center, will also be blinded.

A study flow chart is presented in Appendix [17.1](#), and a flow diagram of subject enrollment and treatment allocation is presented in Appendix [17.2](#). [Table 1](#) through [Table 9](#) in the protocol present the schedule of study procedures to be performed during each the 3 periods in Part A, B, and D of the study.

## 2.4 Treatment Regimens and Randomization

In all three parts of the study, subjects will be randomized to receive either MRT5005 or placebo (normal saline) in a 3:1 ratio. Subjects will receive a single dose in Part A, 5 weekly doses in Part B, and 5 consecutive daily doses in Part D. The 8 mg dose level of MRT5005 will be the SAD starting dose in Part A followed by sequential escalation to the 16 mg and 24 mg dose levels of MRT5005. An additional 20 mg treatment group was added to Part A after blinded safety information from the 24 mg group revealed the occurrence of febrile reactions in 3 of 4 subjects. The 8 mg dose level of MRT5005 will be the MAD starting dose in Part B, followed by sequential escalation to the 16 mg and 20 mg dose levels of MRT5005. An additional 12 mg group was added to Part B to explore the safety profile at an intermediate dose level that was not investigated as a single dose in Part A. The 12 mg dose level may begin enrollment in parallel with the 16 mg dose level. The enrollment and treatment of the 4 subjects within each MAD dose group will be staggered by at least 2 weeks (the next subject in the dose group will only be enrolled and treated when the previous subject has received their second dose and there is approximately 1 week of safety follow-up), with the exception of the 12 mg dose group in Part B which may not require staggered treatment. In Part D, 8 subjects will be randomized in a 3:1 ratio to receive 5 doses of either 4 mg MRT5005 or placebo, administered at 1 dose per day for 5 consecutive days. Because single doses up to 20 mg, as well as 5 weekly doses up to 16 mg have been tolerated in Parts A and B, the enrollment and treatment of the 8 subjects within Part D will not be staggered. During the treatment of subjects in Part D, should AEs occur that indicate the study drug is not tolerated well, the enrollment and treatment of subjects may be terminated by the PSRC and Sponsor, and enrollment and treatment of a lower dose strength may be considered in the remaining subjects in the cohort. For example, if the tolerability of the 4 mg daily dose level is found to be unacceptable, then the 2 mg dose level can be considered for investigation. Subjects will not be allowed to participate in more than 1 part of the study.

## **2.5 Sample Size Determination**

The sample size is not based on any statistical considerations. Instead, the sample size is based on traditional phase 1 first-in-human study designs for this disease population. In Parts A and B of the study, the inclusion of 4 subjects per dose group (3 subjects randomized to MRT5005 and 1 subject randomized to placebo) will provide basic information on safety and tolerability during dose escalation of MRT5005. In Part D, 8 subjects treated at 4 mg MRT5005 or placebo (6 subjects randomized to MRT5005 and 2 subjects randomized to placebo) will provide further safety and tolerability data on MRT5005. This study is also designed with the flexibility to enroll additional groups of subjects to support meeting its objectives.

## **2.6 Protocol Safety Review Committee**

The PSRC will conduct a safety data review before each dose-escalation in Parts A and B and before the initiation of enrollment and treatment of subjects in the first MAD group in Part B. Based on these safety data reviews, the PSRC will decide whether or not to proceed at each of these time points in the study, per Protocol [Sections 3.4.1](#) and [3.4.2](#).

Based on the judgment of the PSRC:

- A Part A dose group may be repeated in a new group of subjects to further assess the safety of the dose level before escalating to the next higher dose level or before multiple dosing is allowed to proceed in Part B.

The PSRC will be notified of all serious adverse events deemed possibly, probably, or definitely related to investigational product (including suspected unexpected serious adverse reaction [SUSAR]) reports in real-time. The PSRC will be notified of 2 occurrences of significant febrile reactions in different participants (defined as  $\geq$  Grade 2 fever [ $>39.0^{\circ}\text{C}$ ] associated with systemic symptomatology [eg, body aches, malaise, nausea]) within 24 hours following administration of IP. If an adverse event of special interest (AESI), as defined in Protocol [Section 8.1.8](#), is reported during the study, the PSRC will be notified by the Sponsor in real-time. The PSRC will receive SAE listings following each dose group and may choose to receive more frequent SAEs listings at any time during the study. The PSRC will also review all available and relevant safety data if stopping criteria are met during the study to determine whether the study will continue or be terminated. The PSRC charter includes the roles and responsibilities of the PSRC, format and structure of PSRC meetings, and details the study stopping criteria.

## **2.7 Dose Group and Study Stopping Criteria and Unblinding**

Investigational product administration will be halted for all subjects in a dose group, as well as any subjects in an ongoing higher dose group if any of the following stopping criteria are met:

- a. Two subjects in a dose group experience a significant febrile reaction (defined as  $\geq$  Grade 2 fever [ $>39.0^{\circ}\text{C}$ ] associated with systemic symptomatology [eg, body aches, malaise, nausea]) within 24 hours following administration of IP.
- b. Two subjects in a dose group experience a suspected moderate to severe allergic/hypersensitivity reaction, including but not limited to anaphylaxis, generalized rash, edema or bronchospasm possibly related to drug treatment.

Investigational product administration will be halted for all subjects in Part D if the following stopping criterion is met:

- a. Three subjects experience Grade 1 fevers (38.0 to  $39.0^{\circ}\text{C}$ ) associated with systemic symptomatology (eg, body aches, malaise, nausea) onset within 24 hours following administration of IP on  $\geq 3$  separate occasions.

Investigational product administration will be halted for all subjects if any of the following stopping criteria are met:

- a. A subject experiences a Grade 4, life-threatening treatment-emergent AE or death that is considered probably or definitely related to investigational product by the Investigator.
- b. Two or more subjects in a dose group experience 1 or more moderate or severe pulmonary exacerbations during the 5-week treatment period in part B or through Day 11 (1 week post-5th dose) in Part D.
- c. Two or more subjects in a dose group experience a decrease in predicted FEV1 of at least 25 % compared to the baseline value (defined as the average of the Day -1 and Day 1 pre-dose values) during the 5-week treatment period in Part B or through Day 11 (1 week post-5th dose) in Part D that cannot be explained, in the opinion of the PI, by the underlying disease of CF and that is confirmed on 2 separate occasions at least 3 days apart.
- d. Two or more subjects in the study experience a suspected serious allergic/hypersensitivity reaction, including but not limited to anaphylaxis, generalized rash or bronchospasm likely to be related to drug treatment.
- e. Two or more subjects in a dose group experience a deterioration in liver function, as detailed below:
  - i. Elevation of ALT or AST to  $>5x$  ULN in a subject regardless of baseline value
  - ii. Elevation of ALT or AST to  $>3x$  ULN in a subject with a normal baseline or elevation of  $>3x$  ULN from the subject's actual baseline if not normal, with the appearance of fatigue, nausea, vomiting, right upper quadrant pain or tenderness, fever, rash, and/or eosinophilia ( $>5\%$ ).
  - iii. Elevation of ALT or AST to  $>3x$  ULN in a subject with a normal baseline or elevation of  $>3x$  ULN from the subject's actual baseline if not normal, and total bilirubin  $>2x$  ULN or INR  $>1.5$ .

To determine whether these stopping rules have been met, the relevant data will be reviewed by the PSRC. To ensure subject safety, the PSRC may request unblinding the treatment assignment(s) for an individual subject or for an entire dose group.

Unless otherwise specified, each display will be presented separately for each study part. For any by study part displays categorized by dose group, summaries will show columns for the 4 mg dose group, 8 mg dose group, 12 mg dose group, 16 mg dose group, 20 mg dose group, 24 mg dose group, and a pooled placebo group, as applicable for each study part. A total column will be displayed where applicable.

Where possible and when specified, integrated displays will be presented combining data from all study parts by treatment (all active MRT5005 treatment dose groups combined, all pooled placebo groups combined).

For any by study part displays categorized by dose group, summaries will show columns for the 4 mg dose group, 8 mg dose group, 12 mg dose group, 16 mg dose group, 20 mg dose group, 24 mg dose group, and a pooled placebo group, as applicable for each study part. A total column will be displayed where applicable.

All data listings and figures will be presented by study part, unless otherwise specified.

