In Part D, 8 subjects will be randomized in a 3:1 ratio to receive 5 consecutive daily doses of either 4 mg MRT5005 or placebo. Enrollment and treatment of subjects will not be staggered. Part D was added to the protocol (Version 5.0 dated 30 July 2020) to evaluate whether febrile reactions observed with higher doses (ranging from 8 mg to 24 mg) of MRT5005 are dose dependent or idiosyncratic.

Investigation of a daily dosing regimen in Part D is attractive given the estimated short half-life of CFTR mRNA (14 hours) and translated CFTR protein (29 hours). The anticipated safety of 4 mg administered daily for 5 days (20 mg total) can be predicted from the safety and tolerability of 20 mg administered as a single dose in Part A.

Enrollment and Treatment of Additional Groups

A SAD dose group may be repeated in a new group of subjects in Part A to further assess the safety of the dose level before escalating to the next higher dose level, or before allowing it to proceed from Part A (SAD) to Part B (MAD).

It is expected that no more than 1 additional group of 4 subjects will be enrolled into the study. Therefore, up to a maximum of 44 evaluable subjects may participate in the study.

Principal/Coordinating Investigators: [REDACTED]

Objectives:

Primary

- The primary objective of the study is to evaluate the safety and tolerability of single and multiple escalating doses of MRT5005 administered by nebulization to adult subjects with CF.

Secondary

- The secondary objective of the study is to evaluate the effect on percent predicted forced expiratory volume in 1 second (ppFEV₁) and other spirometry parameters after single and multiple escalating doses of MRT5005 administered by nebulization to adult subjects with CF.

Rationale:

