The 8, 16, and 24 mg human doses provide lung exposures (0.004, 0.008, and 0.012 mg of [REDACTED] mRNA deposited per g lung, respectively) that are comparable to those of the lower doses given to the rats and non-human primates in the single and multiple-dose toxicity studies (0.19 to 0.77 mg/kg dose levels corresponding to 0.0065 to 0.0154 mg of [REDACTED] mRNA deposited per g lung, and calculated HEDs of 13 to 31 mg). These dose levels deposited significant levels of [REDACTED] mRNA in the lungs of both species compared to endogenous levels and, importantly, expressed detectable levels of human CFTR protein by immunohistochemistry at 24 hours post-treatment. Persistence of the human CFTR protein was also detected in rats at 7 days post-treatment following a single dose of MRT5004 at 0.53 mg/kg (HED of 22 mg); and at 28 days post-treatment following 5 once weekly doses of MRT5005 at 0.77 mg/kg (HED of 31 mg). These observations supported the dose levels and weekly dosing interval of MRT5005 that will be investigated in Parts A and B of this study.

The 4 mg dose strength was selected for evaluation in Part D based on observations of mild to moderate febrile reactions reported in 7 subjects who received a single dose of MRT5005 ranging from 8 to 24 mg (1 subject each in the 8 mg, 16 mg, 20 mg single dose groups in Part A, 3 subjects in the 24 mg single dose group in Part A, 1 subject in the 16 mg multiple dose group in Part B who discontinued treatment after first dose). Evaluation of a lower dose will help determine whether febrile reactions associated with MRT5005 are dose dependent or idiosyncratic. Investigation of a daily dosing regimen in Part D is attractive given the estimated short half-life of CFTR mRNA (14 hours) and translated CFTR protein (29 hours). The anticipated safety of 4 mg administered daily for 5 days (20 mg total) can be predicted from the safety and tolerability of 20 mg administered as a single dose in Part A.

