Treatment-emergent febrile reactions and hypersensitivity reactions will be presented as a count of febrile reactions, febrile reactions by severity, hypersensitivity reactions, and hypersensitivity reactions by severity. Additionally, the table will reflect the count and percentage of subjects experiencing the following: any febrile reaction, any febrile reaction by severity, any hypersensitivity reaction, and any hypersensitivity reaction by severity. The summary will be for all subjects in the safety analysis set by dose group for each study part. In addition, the summary of treatment-emergent febrile reactions and hypersensitivity reactions will be presented for all subjects in the safety analysis set for the study overall by pooled treatment group. Febrile reactions will be identified based on a preferred term of body temperature increased or preferred term of pyrexia within the 24 hours after completion of

nebulization on any dosing day with at least one other systemic symptom reported as a preferred term of headache, arthralgia, myalgia, fatigue, chills, nausea, or vomiting within the 24 hours after completion of nebulization on any dosing day. Severity grade for febrile reactions will be based on the maximum severity of the preferred terms comprising the febrile reaction. Hypersensitivity reactions will be identified based on a preferred term of hypersensitivity within the 24 hours after completion of nebulization on any dosing day.

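### No output in this SAP sets 4 mg beside 8 to 24 mg for febrile reactions: the tables by dose stop at each study part, and the integrated table pools every dose

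*SAP*

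**What the plan says.** **Why Part D exists.** The Protocol Synopsis says that Part D was added "to evaluate whether febrile reactions observed with higher doses (ranging from 8 mg to 24 mg) of MRT5005 are dose dependent or idiosyncratic". Section 2.2.3 repeats the reason: "Evaluation of a lower dose will help determine whether febrile reactions associated with MRT5005 are dose dependent or idiosyncratic". It also counts the earlier reactions: "1 subject each in the 8 mg, 16 mg, 20 mg single dose groups in Part A, 3 subjects in the 24 mg" single-dose group, and one in the Part B 16 mg group, seven subjects in all.

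**How displays are built.** The default in SAP Section 3 is: "Unless otherwise specified, each display will be presented separately for each study part". Integrated displays combine the parts by treatment only: "all active MRT5005 treatment dose groups combined, all pooled placebo groups combined". The programmer notes in the table specifications fix the columns: Part A has 8, 16, 20 and 24 mg; Part B has 8, 12, 16 and 20 mg; Part D has 4 mg and placebo; the overall tables have pooled active and pooled placebo. The listing and figure specifications state that neither is produced across parts.

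**Febrile reactions.** SAP Section 9.4 summarises them by dose group within each part (Table 14.3.2.4). The overall summary "will be presented for all subjects in the safety analysis set for the study overall by pooled treatment group" (Table 14.3.2.5). A reaction is a fever term plus at least one listed systemic symptom in the 24 hours after nebulization ends, whichever dosing day that follows.

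**Size and approach.** SAP Section 2.5 gives Part D as "6 subjects randomized to MRT5005 and 2 subjects randomized to placebo". Protocol Section 9.8 makes all analyses descriptive.

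**The concern.** Whether fever depends on dose is a question about 4 mg against the higher doses. The Part D table alone cannot address it, because its only comparator is two placebo subjects. The integrated table cannot address it either, because it removes dose. The comparison is left to whoever puts three tables together.

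That reader also meets a counting problem. A Part A subject has one chance to be counted as a reactor; a Part B or Part D subject has five. If the 4 mg any-dose rate is set against the Part A single-dose rates, dose is mixed with number of exposures, and the extra chances raise the low-dose figure. A real gradient could look flat. Protocol Section 2.1 says that the study's results will guide dose selection in later trials, so the layout should be settled before the final analysis rather than improvised afterwards.

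**Working it through.** **1. The documents' own figures reproduce.**
- Part D at 3:1: 8 × 3/4 = 6 active and 8 × 1/4 = 2 placebo.
- Febrile subjects before Part D: 1 + 1 + 1 + 3 + 1 = 7.
- Planned active: 12 + 12 + 6 = 30. Planned placebo: 4 + 4 + 2 = 10. Total 40.

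**2. Go through the planned febrile and temperature outputs.**

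| Output | Columns or panels | 4 mg beside a higher dose? |
|---|---|---|
| Table 14.3.2.4, Part A | 8, 16, 20, 24 mg, placebo | No |
| Table 14.3.2.4, Part B | 8, 12, 16, 20 mg, placebo | No |
| Table 14.3.2.4, Part D | 4 mg, placebo | No |
| Table 14.3.2.5, overall | all active, all placebo | No, doses merged |
| Listings 16.2.7.7 and 16.2.7.9 | by part, then dose group | No |
| Figures 14.3.5.1.1 | one plot per dose group within a part | No |

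**3. What the pooled column would show.** Assume planned enrolment, no Part B reactions beyond those in Protocol Section 2.2.3, and x reactors among the six at 4 mg. The pooled active rate is (7 + x)/30:
- x = 0: 7/30 = 23%
- x = 1: 8/30 = 27%
- x = 3: 10/30 = 33%
- x = 6: 13/30 = 43%

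Any placement of the same total across doses gives the same percentage. Further Part B reactions would raise all four.

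**4. What a display by dose would show.** Part A from Section 2.2.3, with 3 active per group: 8 mg 1/3, 16 mg 1/3, 20 mg 1/3, 24 mg 3/3. Together 6/12 = 50%, exact (Clopper-Pearson) 95% interval 21% to 79%. For 4 mg:
- 0/6: 0% to 46%, the upper limit being 1 − 0.025^(1/6) = 0.459
- 1/6: 0.4% to 64%
- 3/6: 12% to 88%

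Even 0/6 overlaps the Part A interval, so the display is informative but not decisive.

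**5. One chance against five.** Suppose each dose carries the same independent chance p of a reaction. This is an assumption; the documents give no per-dose rate. The chance of at least one reaction in five doses is 1 − (1 − p)^5:
- p = 10%: 1 − 0.9^5 = 41%
- p = 20%: 1 − 0.8^5 = 67%

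On these values, a five-dose group would show 41% or 67% against 10% or 20% in a single-dose group with identical per-dose risk.

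**The case against.** **The data are already tabulated.** A reader might infer that the Part D question goes unanalysed. The documents do not support that. Table 14.3.2.4 uses one shell, one definition and one severity rule in all three parts, and it gives every dose, including 4 mg, its own count and percentage. The single-dose gradient from 8 to 24 mg sits in one table. This stands, and it limits the point to a missing comparison.

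**A Day 1 view is planned.** Table 14.3.1.2 has a Study Day 1 page in every part. It works by single preferred term, not the composite reaction, and by calendar day, not the 24-hour window. A fever starting the morning after dosing falls into the next interval, which in Part D (Study Days 2 to 5) also holds doses two to five. It does not replace a first-dose row.

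**Separation by part is defensible.** Randomisation is within dosing group (Protocol Section 6.2.1). Home thermometers came in only for Part B 12 mg, Part B 20 mg and Part D (Protocol Section 12). TRIKAFTA is allowed at entry only in Part D. One column per nominal dose would also merge single-dose and five-dose subjects at 8, 16 and 20 mg. All of this stands. It argues for columns by regimen with a footnote, not against a cross-part table.

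**A trend test is tempting.** Filling in 0/6 at 4 mg and no other reactions gives a one-sided exact permutation trend p of 0.0074 across doses. That is not evidence. Protocol Section 12 lists Part B 12 mg, Part B 20 mg and Part D as still enrolling, so 12 of the 30 active subjects (3 + 3 + 6) are assumed non-reactors, including the very group Part D was to observe. Without those 12 the value is 0.033; in Part A alone it is 0.13. The study is descriptive in any case.

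**Scope.** Dose dependence of fever is a rationale for Part D, not an objective or endpoint in Protocol Sections 2.3 and 2.4. An interim analysis plan is mentioned in Protocol Section 9.5 but not supplied, so the gap is shown for this SAP only. Someone might extend the point to the hypersensitivity table, 14.3.2.7, but the reason given for Part D concerns fever alone.

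**Conclusion.** The point holds as a gap in presentation with a substantive consequence. Febrile rates by dose are planned within each part, but no output in this SAP compares 4 mg with 8 to 24 mg, and the only cross-part febrile table erases dose. The any-dose count, with one opportunity in Part A and five in Parts B and D, means that the by-part tables cannot simply be set side by side.

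The structural finding rests on the documents alone. The illustrative percentages rest on planned enrolment, no further Part B reactions, and the reactions in Protocol Section 2.2.3 meeting the SAP definition. The comparison will be imprecise whatever the layout, with 3 to 6 active subjects per group. The gap does not undermine the safety analysis as a whole, but it is worth closing because it concerns the stated reason for adding a study part.

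**What to change.** Add one descriptive cross-part febrile-reaction table to the SAP, alongside Table 14.3.2.5 or in its place.
- **Columns by dose and regimen:** Part D daily 4 mg; Part A single 8, 16, 20 and 24 mg; Part B weekly 8, 12, 16 and 20 mg; placebo by regimen. Do not merge single-dose and multiple-dose subjects in the any-dose row.
- **Rows:** subjects with a febrile reaction within 24 hours of the first dose, named as the cross-dose comparison, and subjects with a reaction after any dose. Give exact 95% intervals for both.
- **Footnote:** columns from different parts are not randomised against each other, and home thermometers were introduced only for Part B 12 mg, Part B 20 mg and Part D.

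No test is added and Table 14.3.2.7 stays as it is. The cost is one table from data already collected, with no change to conduct. The downside is small cells: 3 to 6 subjects per active column and 2 to 4 per placebo column by plan, so the intervals will be wide and the text should say so.
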